Document Date: 03/25/2019

The Effects of a Jump Rope Exercise Program on Vascular Health, Inflammatory Markers in Prehypertensive Adolescent Girls: full study protocol and statistical analysis plan

NCT#03534427

Study protocol

Participants

Forty girls (age 14-16) volunteered to participate in this research study. All participants were classified as prehypertensive (120-140 mmHg systolic BP and/or 80-90 mmHg diastolic BP) and had abdominal obesity (waist > 80 cm, BMI equal to or greater than the 95th percentile for age and sex). All participants were considered to be inactive, meaning they participated in less than 1 hour of regular physical activity per week within the last 6 months. Other exclusion criteria included a previous musculoskeletal injury within the last year that may negatively affect participation, as well as cardiovascular, pulmonary, adrenal, pituitary, and thyroid diseases. Participants who were already involved in a regular exercise program, on daily medication(s), including antioxidants and fat loss supplements, or weight loss diet plans were also excluded from participation. All procedures performed in this study were in accordance with the ethical standards of the institutional research committee at Pusan National University (PNU IRB/2016_105_HR) and with the tenets of the Declaration of Helsinki. This study was registered in Clinicaltrials.gov (NCT03534427). Informed consent was obtained from all individual participants and their parent/guardian(s) included in this study. Participant characteristics can be seen in Table 1.

Study design

A two-armed, parallel experimental design was used. The jump rope exercise intervention took place during the months of March – June during the school year. Blood samples, anthropometrics, and vascular function parameters were assessed before (baseline) and after the 12-week jump rope exercise program at 8:00 AM (± 1 hour) following an overnight fast. After baseline measurements were performed, the participants were randomly assigned to either the jump rope exercise group (EX, n = 20) or the control group (CON, n = 20). The participants in the EX group participated in an exercise program (50 minutes per day, 5 times per week for 12 weeks) that consisted of jump rope variations. Exercise was performed at 2:00PM (± 1 hour) Monday-Friday. The EX group did not perform any additional exercise outside of this prescribed program during the 12 weeks. The participants in the CON group did not participate in the exercise intervention, or any outside exercise during the 12-week period, but were present and supervised in the laboratory at the same frequency, duration, and time of day as the EX group throughout the entire study period. Both groups of participants were advised weekly not to change their diet habits (~1920 kcal/day) for the duration of the study, and diet logs were obtained every week to keep track of dietary intake. Water intake was not recorded, however, participants were encouraged to consume approximately 2.5 liters of water per day (Sawka et

al. 2005). All exercise sessions were supervised by trained professionals and all measurements were taken by qualified researchers.

Blood sampling and analysis

Blood samples were collected at 8:00 AM (± 1 hour) after an overnight fast at baseline and after 12 weeks from an antecubital vein. Each sample was centrifuged for 15 minutes at 3,000 rpm stored at -80°C for later analysis. Using the provided reagents, each blood sample was run in duplicate in accordance with the manufacturer's instructions for total nitrate and nitrite levels, which were analyzed using a Griess assay kit from Cayman Chemical (Ann Arbor, MI, USA) (Giovannoni et al. 1997). The amount of nitrate and nitrite produced in the reaction mixture was determined spectrophotometrically at 540 nm (OD540) using a microplate reader (Edwards et al. 2004; Masaki and Yanagisawa 1992). Levels of endothelin-1 (ET-1) in blood samples were measured with an enzyme immunoassay kit (Endothelin-1 Enzyme Immunoassay Kit, Cayman Chemical, Ann Arbor, MI, USA). The detection range for ET-1 using this assay was from $\geq 1.5 \mu\text{mol/mL}$ (Hodeib et al. 2010). C-reactive protein (CRP) was assessed using an enzyme immunoassay kit (C-Reactive Protein Enzyme Immunoassay Kit, Cayman Chemical, Ann Arbor, MI, USA) according to the manufacturer's instructions (Druwe et al. 2012).

Pubertal Development

Pubertal development was assessed using Tanner staging (breast and pubic hair stage) by self-reporting at the beginning of the study. Standard line drawings and written descriptions were provided, and participants selected the picture that most accurately reflected their appearance (Morris and Udry 1980).

Anthropometrics

Anthropometric measurements were taken at baseline and after 12 weeks. Height was measured without shoes using a stadiometer to the nearest 1.0 cm. Body composition was measured using bioelectrical impedance analysis (BIA) (InBody 230, Biospace, Seoul, Korea), which simultaneously recorded total body mass (nearest 0.1kg), percent body fat (nearest 0.1%), and fat-free mass (nearest 0.1 kg) (Seo et al. 2012). The InBody 230 specifically has been validated to be consistent with the doubly labeled water method (Beato et al. 2018) and dual x-ray absorptiometry for measurements of total fat mass, total lean mass, and percent body fat (Karelis et al. 2013). For BIA, the intra-assay coefficient of variation (repeated measures within individual) was $0.8 \pm 0.9\%$ and the inter-assay coefficient of variation (repeated measures between different days) was $0.3 \pm 0.2\%$. BMI was calculated as body mass divided by the square of height (kg/m^2). Waist circumference was recorded using a standard tape measure to the nearest 0.1 cm

at the midpoint between the iliac crest and the lower rib. These values were used to determine adiposity in absolute terms; however, there are no standard values that are considered to represent high adiposity in children and adolescents (Flegal et al. 2010).

Vascular function

Resting systolic and diastolic BP (mmHg) and resting heart rate (bpm) were both measured in duplicate using an automatic sphygmomanometer (HEM-7113 INT; Omron Corp., Kyoto, Japan) and radial artery palpation, respectively, at baseline and after 12 weeks. The measurements were recorded after participants were in a seated position for 5 minutes. The average of the two measurements was recorded as the resting BP and resting heart rate. Brachial-to-ankle pulse wave velocity (baPWV, m/s), an indicator of peripheral arterial stiffness, was measured using applanation tonometry (SphygmoCor CPV system, AtCor Medical Ltd, Sydney, Australia), followed by data analysis (version 8.0, SphygmoCor Cardiovascular Management Suite, AtCor Medical Ltd, Sydney, Australia). Two measurements were collected, one at each time point, and averaged as previously described (Weber et al. 2004; Yambe et al. 2007).

Jump rope exercise program

Participants in the EX group participated in a jump rope exercise program for 12 weeks, 5 days per week, for 50 minutes per day (Table 2). This program was divided into a warm-up (5 minutes), the main exercise session (40 minutes of rope jumping variations), and a cool-down (5 minutes). Both the warm-up and the cool-down consisted of stretching, walking, and jogging. There were 7 main rope jumping exercises, including 1 line 2 jump, jumping feet together, running jumping, open side jump, open back and forth jump, and rock paper scissor jump. The jump rope exercise program intensity incrementally increased every 4 weeks: weeks 1-4 were at 40-50% HRR and 11-12 RPE, weeks 5-8 were at 50-60% HRR and 13-14 RPE, and weeks 9-12 were at 60-70% HRR and 15-16 RPE. These exercise intensities, frequencies, and durations were chosen to reflect previous studies that reduced fat mass, BP, and arterial stiffness in various populations (Arikawa et al. 2011; Beck et al. 2013; Ewart et al. 1998). The exercise intensity of the jump rope program was monitored using heart rate reserve (HRR) and Borg's rating of perceived exertion scale (RPE) of 6-20. Participant heart rate was monitored using a wearable Polar heart monitor (Electro, Oy, Kempele, Finland) during all exercise sessions in order to sustain the proper training intensity. There were 5 trainers supervising each exercise session, each specifically assigned to 4 participants. Heart rate monitors and RPE

were checked every 5 minutes during the 40-minute training session. If heart rate or RPE were either too low or too high, participants were encouraged to either increase or decrease their effort during the session.

Statistical analysis plan

The Shapiro-Wilk test was used to determine the normality of the data. Independent t-tests were used to determine baseline differences between the two groups. A two-way analysis of variance (ANOVA) with repeated measures [group (CON and EX) x time (before and after 12 weeks)] was used to compare the difference of changes between pre- and post-jump rope exercise program within and between groups on the dependent variables. Bonferroni correction was used to determine the effects of the jump rope training program over time. When a significant main effect or interaction was noted, paired t-tests were used for post-hoc comparisons. An effect size analysis was performed using eta-squared (η^2) for the two-way ANOVA, and interpreted 0.01, 0.06, and 0.14 as small, medium and large, respectively (Lee et al. 2018). Cohen's d was used for the t-tests, interpreted as 0.20, 0.50, and 0.80 as small, medium and large, respectively (Lee et al. 2018). All analyses were performed using SPSS 25.0 (SPSS Inc., Chicago, IL, USA). Data are presented as Mean \pm SD. Statistical significance was set at $P \leq 0.05$. It was estimated that 40 participants would enable 80% power to detect a 5% decrease in baPWV after the jump rope exercise program based on previous literature (Figueroa et al. 2011).

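### Baseline baPWV is measured before allocation, but the planned analysis does not adjust for it and relies on baseline t-tests that lead to no action

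*Combined protocol and SAP*

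**What the plan says.** The Study design section fixes the order of events. "Blood samples, anthropometrics, and vascular function parameters were assessed before (baseline) and after the 12-week jump rope exercise program", and then: "After baseline measurements were performed, the participants were randomly assigned to either the jump rope exercise group (EX, n = 20) or the control group". Nothing further is said about allocation: no method of generating the sequence, no holder of it, no concealment, and no blocks, strata or minimisation.

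The Statistical analysis plan uses the baseline in two ways. First, "Independent t-tests were used to determine baseline differences between the two groups", with no statement of what follows if a difference is found. Second, baseline is the first time point of a two-way repeated-measures ANOVA (group by time) that "was used to compare the difference of changes between pre- and post-jump rope exercise program within and between groups on the dependent variables". No baseline covariate appears in any model. The sample-size sentence names baPWV as the outcome for which 40 participants give 80% power, for a 5% decrease.

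**The concern.** When baseline precedes randomisation in a trial of 40, the baseline value of each outcome is free information for the analysis. This plan uses it in a weak form. With only two time points, the group-by-time interaction is algebraically the t-test on change scores. Subtracting the baseline in full over-corrects whenever the pre-post correlation is below 1: an arm that starts higher by chance is expected to fall more, with no treatment effect. Part of any chance gap in baseline baPWV therefore appears as an apparent difference in change.

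The baseline t-tests do not deal with this. They alter nothing in the model, and at 20 per arm a gap large enough to matter can easily be non-significant and be read as balance. At stake are avoidable imprecision in the main comparison and a single realised result that is harder to interpret if the arms happen to differ at baseline.

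**Working it through.** **Inputs from the documents.** 20 per arm (Study design); significance level 0.05, 80% power, 5% decrease in baPWV (Statistical analysis plan).

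**Assumptions.** Two-sided test; normal baPWV with equal SD before and after; linear pre-post relation. The correlation rho is not given, so 0.5, 0.7 and 0.9 are shown. Gaps are in units of the baseline SD.

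**The plan's own figure.** The 80% power cannot be reproduced, because no SD is stated. Working backwards, 20 per arm with a two-sample t-test detects d = 0.909 SD of change. A 5% decrease then needs an SD of change of 5/0.909 = 5.5% of baseline.

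**Size of the chance gap.** SD of the difference in baseline means = sqrt(2/20) = 0.316.
- P(gap above 0.3 SD, either direction): 0.3/0.316 = 0.95, giving 34%.
- P(gap above 0.5 SD, either direction): 0.5/0.316 = 1.58, giving 11.4%.

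**What the baseline t-test would show.** With 38 degrees of freedom the critical value is 2.024, so a gap must reach 2.024 × 0.316 = 0.64 SD to be significant. A 0.5 SD gap gives t = 1.58, p = 0.12.

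**Effect on the planned comparison.** Expected shift in the difference of changes = (1 − rho) × gap. The detectable difference in baseline SD units = 0.909 × sqrt(2(1 − rho)). For a gap of 0.5 SD:

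| rho | Shift (SD) | Detectable difference (SD) | Shift / detectable | Type I error given a gap above 0.5 SD (simulated) |
|---|---|---|---|---|
| 0.5 | 0.25 | 0.909 | 27% | 13.8% |
| 0.7 | 0.15 | 0.704 | 21% | 9.7% |
| 0.9 | 0.05 | 0.407 | 12% | 5.9% |

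Over all randomisations, simulated type I error was 5.2%, 5.0% and 4.8%, i.e. the nominal 5%.

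**Gain from adjustment.** Change-score variance is proportional to 2(1 − rho), ANCOVA variance to 1 − rho², so the ratio is (1 + rho)/2. Estimating the slope with 40 girls multiplies the ANCOVA variance by about 1 + 1/36 = 1.028.

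| rho | Ratio, theory | Ratio at n = 40 | Power if change score has 80% (theory) | Same, n = 40 and 37 df |
|---|---|---|---|---|
| 0.5 | 0.75 | 0.77 | 90% | 89% |
| 0.7 | 0.85 | 0.87 | 86% | 85% |
| 0.9 | 0.95 | 0.98 | 82% | 81% |

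**What stratified allocation would add.** Simulated randomisation 5:5 within four baseline-baPWV strata of 10 cuts the gap SD from 0.316 to 0.122, and P(gap above 0.3 SD) from 34% to 1.5%. Once the analysis is ANCOVA, the further saving is only about 1 to 3 percentage points of the change-score variance.

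**The case against.** The strongest reply is that nothing here is invalid. Simple randomisation of 40 is legitimate, and measuring first is good practice because baseline readings cannot be coloured by knowledge of the arm. The change-score test keeps its 5% error rate, and chance imbalance is already part of its variance. The change score also removes the rho share of any gap. The 12–27% shifts apply only to a 0.5 SD gap, and gaps that large or larger have an 11% chance. At rho = 0.9 the gain from adjustment is about 2%. All of this stands, and it limits the point to efficiency and to the realised comparison.

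A reader might go further and infer that allocation was unconcealed, that it ignored the baseline values, or that girls were steered to an arm by staff who held every baseline result. The documents do not support this. They are silent on method, and silence is not evidence of a defect. The blood samples were frozen for later analysis, so nitrate/nitrite, ET-1 and CRP results need not have existed at allocation. Arm sizes are equal as stated. The trainer numbers ("There were 5 trainers supervising each exercise session, each specifically assigned to 4 participants", so 5 × 4 = 20, the whole exercise arm) suggest the arm could run as one class and be allocated in one step. In that case no later enrolment could be influenced by a guessed sequence. What remains is a reporting gap: concealment cannot be judged from the text, and no analysis could replace it if it were absent.

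**Conclusion.** The point holds as a low-cost improvement to the analysis, not as a finding of bias. Under equal SDs and a linear pre-post relation, ANCOVA reduces the variance of the baPWV comparison by about 23%, 13% and 2% at correlations of 0.5, 0.7 and 0.9 with 40 girls, and removes the expected shift from a chance baseline gap. The correlation is assumed throughout, and a high value makes the gain small. The baseline t-tests serve no purpose in the plan as written, since no decision depends on them. Type I error is not inflated overall. The undocumented sequence and concealment are a separate matter of reporting, with no computable size.

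**What to change.** In the Statistical analysis plan, replace the baseline t-tests and the group-by-time test with ANCOVA of the 12-week value on group and the baseline value of the same outcome. Do this for each outcome, with baPWV first, and report the adjusted between-group difference with its confidence interval. Show baseline values by arm descriptively, without P values. Because the group-by-time test now triggers the paired post-hoc t-tests, state that any within-arm changes are descriptive. The cost is one degree of freedom per model and a few lines of text, with no new data.

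In Study design, report how the sequence was generated, who held it, whether it was concealed until all baseline measurements were complete, and whether any baseline value was used.

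The text is in the past tense, so allocation has probably taken place and only analysis and reporting can change. If it has not, randomising 5:5 within four strata of baseline baPWV is an optional, cheap addition. It would improve visible balance on baPWV and its correlates, would add little precision once the analysis is adjusted, and would have to wait for the last baseline visit.

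### The plan states no blinding to arm for the operator-dependent week-12 measures (tonometry-based baPWV, tape waist, palpated pulse)

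*Combined protocol and SAP*

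**What the plan says.** **Staff.** The only sentence on who measures is in the Study design section: "All exercise sessions were supervised by trained professionals and all measurements were taken by qualified researchers". The Jump rope exercise program section adds: "There were 5 trainers supervising each exercise session, each specifically assigned to 4 participants". Control girls "were present and supervised in the laboratory at the same frequency, duration, and time of day as the EX group", but the staff who supervised them are not identified.

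**Sequence.** "After baseline measurements were performed, the participants were randomly assigned to either the jump rope exercise group (EX, n = 20) or the control group". Outcomes are measured again after 12 weeks.

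**Methods.** Under Vascular function, baPWV "was measured using applanation tonometry (SphygmoCor CPV system", with a separate software analysis afterwards. Resting pulse is palpated at the radial artery, and BP is taken by an automatic device. Under Anthropometrics, "Waist circumference was recorded using a standard tape measure", and body composition is by bioelectrical impedance.

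**Analysis.** The Statistical analysis plan tests group × time by repeated-measures ANOVA and justifies 40 participants by 80% power for a 5% fall in baPWV.

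No section mentions blinding or masking of assessors, of those analysing the tonometry, or of laboratory staff.

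**The concern.** The girls cannot be blinded to a jump rope programme, so protection against biased measurement has to come from the people who take and process the readings. The plan states no such protection for week 12.

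Three measures leave room for judgement: tonometry (probe handling, which recordings are accepted, the later software step), waist (tape placement and tension) and pulse (counting by hand). The first matters most, because baPWV is the only outcome named in the power statement and its planned effect is just 5%.

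A reader who knows the arm and expects exercise to help could shift week-12 readings slightly. Such a shift would look exactly like a treatment effect.

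**Working it through.** **1. Where a reading error would go.** Write each girl's change as week 12 minus baseline. Baseline is read before assignment, so its error cannot depend on arm. If week-12 readings carry a systematic between-arm difference *b*, then

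expected difference in mean change (EX − CON) = true effect + *b*.

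With two groups and two time points, the ANOVA interaction is equivalent to a two-sample t-test on the changes, so it estimates this sum. Nothing in the data separates the two terms.

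**2. Inputs.**
- Arms of 20 and 20 (Study design), so df = 38.
- Significance level 0.05 (Statistical analysis plan). Sidedness is not stated; two-sided is assumed, critical t = 2.024.
- Target: a 5% fall in baPWV with 80% power from 40 participants (Statistical analysis plan).
- SD of change: not given. Assumed, with a range.
- Reading bias *b*: not given. Assumed at 1 and 2 percentage points of baseline, which is 1/5 = 20% and 2/5 = 40% of the target.

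**3. The plan's own figure.** Without an SD, the 40 can be neither confirmed nor refuted. Solving backwards for the SD that gives 80% power:
- two-sample t-test, 20 per arm: standardised effect 0.909, so SD = 5/0.909 = 5.5% of baseline (normal approximation: 5/0.886 = 5.6%);
- paired within-arm test, n = 20: 5/0.660 = 7.6%;
- paired test, n = 40: 5/0.454 = 11.0%.

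The power statement does not say which comparison it refers to, so the SD range below runs from 4% (a value below all of these) to 11%.

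**4. False-positive rate under bias.** With no true effect, the standard error is SD × √(2/20), the noncentrality is δ = *b*/SE, and the rejection rate is P(|T| > 2.024) for a noncentral t with 38 df.

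| Assumed SD of change | SE | δ, 1-point bias | Rejection | δ, 2-point bias | Rejection |
|---|---|---|---|---|---|
| 4% | 1.265 | 0.791 | 12.0% | 1.581 | 33.8% |
| 5.5% | 1.739 | 0.575 | 8.7% | 1.150 | 20.2% |
| 8% | 2.530 | 0.395 | 6.7% | 0.791 | 12.0% |
| 10% | 3.162 | 0.316 | 6.1% | 0.632 | 9.5% |
| 11% | 3.479 | 0.287 | 5.9% | 0.575 | 8.7% |

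Check: at SD 5.5% and a true effect of 5, δ = 5/1.739 = 2.875, which returns 80% power.

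**5. Effect of blinding on the design figures.** None. The sample size stays at 40 and the nominal level at 0.05.

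**The case against.** The strongest case against has four parts.

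**Silence is not evidence of unblinded assessment.** A reader might infer that the week-12 assessors knew the arm. The documents do not say so. Sessions ran at about 2 PM and measurements at about 8 AM, so measuring researchers need not have seen who exercised. Equally, nothing says they were kept away from sessions or from the allocation. This objection stands: the finding is that no safeguard is stated, and that a reader cannot tell.

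**The staffing is unknown.** A reader might also infer that the plan already separates trainers from measuring researchers, so that blinding would need no extra people. The Study design sentence gives two role labels; it does not say the groups do not overlap. The number of measuring researchers and the staffing of control sessions are not given. If one team did both jobs, keeping session staff off measurement would need new people. This stands for the face-to-face measures. It does not touch the software analysis, which can be coded whoever runs it.

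**The magnitude is conditional.** The single pair 8.7% and 20.2% holds only if the power statement refers to a between-arm comparison with an SD of change near 5.5%. This stands, which is why a range is given.

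**Several outcomes carry little reading risk.** BP is automatic, body composition is by impedance, and the blood markers are read by plate reader or kit assay. This stands too. The point is confined to tonometry, waist and pulse, and coding of blood samples is offered only as an optional addition.

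**Conclusion.** The concern holds in this limited form: the plan states no blinding to arm for week-12 tonometry, waist and palpated pulse, and its two staff labels do not fill that gap. Because baseline is protected by its place before randomisation, any arm-dependent error at week 12 biases the group × time contrast in full, and the planned ANOVA can neither detect nor remove it.

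How much this matters is not known from the documents. The calculated false-positive rates rest on an assumed bias, an assumed SD, a two-sided test and no true effect. They show that a bias equal to a fifth of the planned effect does modest harm and one equal to two-fifths can do serious harm if the SD is small. They are not estimates of what happened in this trial.

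This is a cheap improvement worth making. It is not proof of a biased result.

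**What to change.** **Offline steps.** Give the baPWV recordings that have been kept codes carrying neither arm nor time point. Run the SphygmoCor software analysis on the codes and lock the results before unblinding. The frozen blood samples can optionally be coded in the same way before assay.

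**Face-to-face measures, where the existing roster allows.** Staff who supervised either arm's sessions take no week-12 outcome measurement, and the measuring researchers are not told the arm.

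**Visits already complete.** The document is dated 03/25/2019 and written in the past tense, so roster rules may come too late. In that case, apply the coding to stored recordings and samples, state who measured at week 12, whether they also supervised sessions and whether they knew the arm, and report a limitation if they did.

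**Cost.** A little coding work, with no change to sample size or significance level. Whether the roster rule needs more people cannot be judged from the documents. Coding protects the software step but not probe handling, and blinding of the face-to-face measures may remain imperfect because a girl can reveal her arm.

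### BP defines entry and is an outcome, but the only BP procedure described is one duplicate seated measurement per time point, and how entry BP was established is not stated

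*Combined protocol and SAP*

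**What the plan says.** Participants makes raised BP a condition of entry: "All participants were classified as prehypertensive (120-140 mmHg systolic BP and/or 80-90 mmHg diastolic BP". It does not say when, how or on how many occasions this was established.

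Vascular function gives the only BP procedure: "Resting systolic and diastolic BP (mmHg) and resting heart rate (bpm) were both measured in duplicate using an automatic sphygmomanometer", with palpation for heart rate. "The measurements were recorded after participants were in a seated position for 5 minutes", and then "The average of the two measurements was recorded as the resting BP and resting heart rate". The text does not use the word sitting, but one sitting per time point is the natural reading.

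Study design sets the two time points: "Blood samples, anthropometrics, and vascular function parameters were assessed before (baseline) and after the 12-week jump rope exercise program", at 8:00 AM (± 1 hour) after an overnight fast. No separate screening visit is described. Girls were then "randomly assigned to either the jump rope exercise group (EX, n = 20) or the control group (CON, n = 20").

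The statistical analysis plan applies "A two-way analysis of variance (ANOVA) with repeated measures [group (CON and EX) x time (before and after 12 weeks")] to the dependent variables, which include BP. It follows any significant main effect or interaction with paired t-tests. The power statement concerns baPWV only. A between-day coefficient of variation is reported for body composition (Anthropometrics), but none for BP.

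**The concern.** Two readings taken minutes apart share the same day. Averaging them reduces reading error and leaves day-to-day variation as it was. Three things follow.

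- **Who is in the trial.** A girl whose usual SBP is below 120 can qualify on a high day. The title and the entry rule then describe the sample less well than they claim.
- **Precision.** Each BP change carries the day-to-day error of two single days, which widens the between-arm comparison.
- **Regression to the mean.** If the reading that admitted a girl is also her baseline value, it is high partly by chance and will fall at 12 weeks in both arms. Randomisation and the control arm protect the group x time test. They do not protect the time main effect or a paired t-test within one arm, and the analysis plan lets the first trigger the second.

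**Working it through.** **Plan's own figure.** There is none for BP. The stated 80% power with 40 girls is for a 5% fall in baPWV and comes without an SD. With 20 per arm, two-sided 5%, it is met only if the SD of change is about 5.6% of baseline (normal approximation; 5.5% on the t distribution). It says nothing about BP.

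**Inputs from the document.** SBP entry range 120-140 mmHg; 20 per arm; baseline and 12 weeks; P ≤ 0.05 (two-sided assumed).

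**Inputs assumed.** Population mean SBP μ = 115-118; between-girl SD s_b = 8-9; day-to-day SD s_w = 5-8, taken as the whole error of one sitting's mean; SD of true change 3; between-arm difference 5 mmHg. Entry is on SBP only; the DBP route is not modelled.

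**Step 1: why duplicates do not settle it.** Error variance of one sitting's mean = day variance + reading variance/2. With a day SD of 6 and a reading SD of 4 this is 36 + 16/2 = 44. Even perfect readings would leave 36. Averaging over two days halves the whole 44, to 22.

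**Step 2: mislabelling and untreated fall.** True SBP ~ N(μ, s_b²); observed = true + N(0, s_w²/k) for k days; select observed values of 120-140. Simulation with 2,000,000 girls per setting:

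| μ / s_b / s_w | True SBP < 120, one day | True SBP < 120, two-day mean | Fall at retest, one day (mmHg) |
|---|---|---|---|
| 118 / 8 / 5 | 23% | 17% | 2.4 |
| 115 / 9 / 5 | 27% | 20% | 2.7 |
| 118 / 9 / 7 | 28% | 21% | 3.5 |
| 115 / 9 / 7 | 36% | 27% | 4.4 |
| 115 / 9 / 8 | 40% | 30% | 5.3 |

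Check by formula for 115/9/7: fall = s_w²/(s_b² + s_w²) × (mean of selected − μ) = 49/130 × (126.76 − 115) = 0.377 × 11.76 = 4.4.

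A wider grid (μ 112-124, s_b 8-10, day SD 4-8, reading SD 4) gives 11-58% on one day.

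**Step 3: power of the between-arm comparison.** SD of change = √(2 s_w²/k + 3²). Noncentrality = 5 / (SD of change × √(2/20)), with 38 df. For s_w = 7, one day: √(98 + 9) = 10.34; 5/(10.34 × 0.316) = 1.53; power 32%.

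| s_w | SD of change, 1 day → 2 days | Power, 1 day → 2 days | Relative loss on 1 day |
|---|---|---|---|
| 5 | 7.68 → 5.83 | 52% → 75% | 31% |
| 6 | 9.00 → 6.71 | 40% → 63% | 37% |
| 7 | 10.34 → 7.62 | 32% → 53% | 40% |
| 8 | 11.70 → 8.54 | 26% → 44% | 41% |

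**Step 4: within-group tests with no treatment effect, entry reading reused as baseline.** With 20 girls, the paired t-test on SBP change rejects in about 33-59% of simulated trials under the step 2 settings, and in 11-65% in a separate simulation with other inputs. The between-arm comparison of changes rejects in about 4-5%, as it should.

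**The case against.** **The sizes are assumed.** The document gives no BP mean, SD, day-to-day SD or target difference. This stands: only the direction follows from the text, and the wider grid shows how far the share can move. Some of the girls counted are only just below the cut-off; 9-24% have a true SBP below 117. The power formula also ignores that selection on the baseline reading narrows its error. If entry and baseline are the same reading, the SD of change at s_w = 7 is 9.6 rather than 10.3, and one-day power over the range is 30-56% rather than 26-52%. That is a small difference.

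**Entry reading and baseline.** A reader might infer that the value that admitted a girl is also her baseline. The document describes no other reading, but neither does it exclude one. The untreated fall and step 4 are therefore conditional. What is certain is that the method of establishing entry BP is not reported.

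**Power halved.** A reader might infer that measuring on one day halves the power. Step 3 does not support this: against two days the relative loss is 31-41%.

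**Extra readings almost free.** Control girls "were present and supervised in the laboratory at the same frequency, duration, and time of day as the EX group", so a reader might infer that a second reading could be taken at sessions already scheduled. Those sessions are at 2:00 PM (± 1 hour) and run during the programme, after assignment. Outcome testing is at 8:00 AM, fasting. A comparable second reading needs another morning visit.

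**Limited consequence.** The fixed hour, fasting, five-minute rest and duplicate readings already remove some noise. Randomisation after baseline, with a concurrent control, leaves the group x time test unbiased. Two days remove only about a quarter of the mislabelling. All of this stands. The point concerns precision and description, not the validity of the between-arm test.

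**Conclusion.** The point holds as a design and reporting weakness. Raised BP defines the population and BP is an outcome, yet one duplicate measurement per time point is all that is described, and the basis for entry is not given. Under the stated assumptions (SBP route only), 23-40% of enrolled girls could have a true SBP below 120, against 17-30% on a two-day mean. One-day power for an assumed 5 mmHg difference is about a third to two-fifths below two-day power. If, and only if, the entry reading is also the baseline, an untreated fall of 2.4-5.3 mmHg is expected in both arms, and a significant within-arm fall would not be evidence of an exercise effect.

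A reader might infer that the between-arm BP result is biased or that 40 girls is the wrong number. Neither follows: the group x time test is protected by randomisation, BP is not named as primary, and the stated sample size rests on baPWV.

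**What to change.** 1. State how and on how many days entry BP was established, and whether that reading is also the baseline value.
2. Take duplicate seated BP on two separate mornings at baseline, before assignment, and on two mornings at 12 weeks, at the same clock time and the same interval from any exercise session in both arms. Analyse the two-day mean.
3. Where a separate entry reading exists, use it for entry only and not as the baseline outcome. If the two-day mean serves both purposes, some regression remains: 1.3-3.2 mmHg under the same assumptions.
4. Rest BP conclusions on the group x time comparison, not on paired t-tests within an arm.

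**Cost.** One extra short morning visit per girl at each time point: 40 × 2 = 80 sittings, with the existing device and staff, beside 5 × 12 = 60 scheduled sessions per girl. A few more girls would need screening, because some will not qualify on a two-day mean. The gain is mainly in precision; mislabelling is reduced, not removed.

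The document is written in the past tense. If data collection is complete, items 1 and 4 can still be done at no cost, and items 2 and 3 apply to any repeat of the trial.
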